for 10 seconds. We will use implicit feedback, in which subjects are kept unaware of the purpose of feedback, in order to more confidently attribute changes in behavior to modification of brain network dynamics by minimizing the use of explicit cognitive strategies and instead focusing on targeted neural processing[41]. This also avoids complicated instructions, reducing potential experimenter effects. Implicit feedback has been found to be robust and may be advantageous over explicit feedback[41]. The instructions will be, "Try methods that you have found to help you not use opioids or cope with craving in the past. The main thing is to try different strategies and see what works the best for you." Participants will be debriefed after each scan to ask whether they felt that they could control the feedback, and what strategies they used to try to control the feedback. This approach has been used previously including in our own work. [2-6] Transfer runs will be used to test control of the opioid abstinence network without feedback and will be exactly the same as feedback runs with the exception that a fixation cross will be displayed instead of the feedback bar. Subjects will be shown the same arrow cues and given the same instructions to increase the feedback bar.

Hypothesis testing: Network connectivity strength assessed at each scanning session will be entered into SPSS to test the following Specific Aims:

Aim 1: *To determine if connectome-based neurofeedback is associated with reduced opioid use compared with sham feedback.* H1a. Subjects receiving active versus sham feedback will report lower levels of opioid use from baseline to follow-up scans. H1b. This reduction will persist over time, as indicated by reduced opioid use through 1-mo follow-up.

Approach: Opioid use will be monitored by weekly urinalysis and TLFB across the five weeks from baseline to follow-up scans and measured as % negative urines (H1a); or will be measured using TLFB at 1-mo follow-up with abstinence at 1-mo confirmed by urinalysis (H1b). Medication compliance will be tracked via clinic records. Opioid use will be entered into a linear effects model with the between-subject factor of feedback group (active/sham).

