Aim 2: *To determine if connectome-based neurofeedback is associated with changes in intrinsic connectivity.* H2a. Subjects receiving active versus sham feedback will show increased opioid abstinence network connectivity between resting state acquired at follow-up versus baseline scans. H2b. This effect will generalize to increased connectivity during fMRI reward and cognitive tasks as in our pilot data.

Approach: Opioid abstinence network connectivity strength will be calculated during resting state (H2a), MIDT and Stroop tasks (H2b) as in our pilot data, and will be entered into a linear mixed effects model with the between-subject factor of feedback group (active/sham) and the within-subject factor of time (baseline/follow-up scans).

Aim 3: *To determine if connectome-based neurofeedback is associated with greater improvements in clinical features of OUD than sham feedback.* H3a. Subjects receiving active versus sham feedback will show reduced craving and negative affect at follow-up versus baseline scans. H3b. Increased opioid abstinence network connectivity during transfer runs will be correlated with reduced craving and negative affect.

Approach: Craving (Opioid Craving Scale) and negative affect (Quick Inventory of Depressive Symptomatology) will be calculated at follow-up and baseline scans and compared between groups using repeated measures analysis of variance. Change in opioid abstinence network connectivity strength will be calculated during transfer runs at baseline and follow-up scans. We will test for Pearson's correlations between change in connectivity strength and changes in craving and negative affect.

5. **Genetic Testing** N/A

6. **Subject Population:** Provide a detailed description of the types of human subjects who will be recruited into this study.

IRB# 2000025618

Write here

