This protocol presents minimal risks to the subjects and Unanticipated Problems Involving Risks to Subjects or Others (UPIRSOs), including adverse events, are not anticipated. In the unlikely event that such events occur, Reportable Events (which are events that are serious or life-threatening and unanticipated (or anticipated but occurring with a greater frequency than expected) and possibly, probably, or definitely related) or Unanticipated Problems Involving Risks to Subjects or Others that may require a temporary or permanent interruption of study activities will be reported immediately (if possible), followed by a written report within 5 calendar days of the Principal Investigators becoming aware of the event to the IRB (using the appropriate forms from the website) and any appropriate funding and regulatory agencies. The investigators will apprise fellow investigators and study personnel of all UPIRSOs and adverse events that occur during the conduct of this research project through regular study emails or via email as they are reviewed by the principal investigators. The protocol's research monitor(s), study sponsors, funding and regulatory agencies, and regulatory and decision-making bodies will be informed of serious and unanticipated and related adverse events or unanticipated problems involving risks to subjects or others will be reported adverse events within 5 days of the event becoming known to the principal investigator.

13. Statistical Considerations: Describe the statistical analyses that support the study design.

Write here

Our previous neurofeedback work showed that data from 10-20 subjects is adequate for demonstrating significant control of activity in a single brain region[13, 65, 68, 69] and that data from two groups of 10-20 subjects is adequate for detecting group differences in control of activity[13, 68]. Our prior CPM work showed that data from N=10 per group is sufficiently powered

IRB# 2000025618

(>.90) to detect differences in connectome-based networks (noncentrality parameter (δ)=5.36, critical t-value=2.10, df=18, power (1- β)=0.99). Finally, we have established retention rates of >85% over 3-months for fMRI studies with methadone patients[10, 70]. Thus, we are confident that a sample size of N=24 (N=12 per group) is sufficiently powered.

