The statistical tests will be as follows: Aim 1: Opioid use will be entered into a linear effects model with the between-subject factor of feedback group (active/sham). Aim 2: Opioid abstinence network strength during resting state and task fMRI runs will be compared between time points using linear mixed models with the between-subject factor of group (active/sham) and the within-subject factor of time (baseline/follow-up scan). Aim 3: Craving and negative affect will be compared using linear mixed effects model with the between-subject factor of group (active/sham) and the within-subject factor of time (baseline/follow-up scan). Associations between craving and negative affect and opioid abstinence network connectivity strength during transfer runs will be tested using Pearson's or Spearman's correlations, as appropriate depending on the distribution of the data. Replication: For replication of our pilot data (Figure 2 of research strategy), Pearson's correlations will be tested between opioid abstinence network connectivity strength at baseline and percent opioid-negative urines across the study.

SECTION II: RESEARCH INVOLVING DRUGS, BIOLOGICS, RADIOTRACERS, PLACEBOS AND DEVICES

If this section (or one of its parts, A or B) is not applicable, check off N/A and delete the rest of the section.

A. RADIOTRACERS N/A

B. DRUGS/BIOLOGICS N/A

C. DEVICES N/A

SECTION III: RECRUITMENT/CONSENT AND ASSENT PROCEDURES

1. Targeted Enrollment: Give the number of subjects:

- a. Targeted for enrollment at Yale for this protocol:
24 completers (individuals participating in all scanning sessions).
- b. If this is a multi-site study, give the total number of subjects targeted across all sites: NA

2. Indicate recruitment methods below. Attach copies of any recruitment materials that will be used.

 Flyers	 Internet/web postings	 Radio
 Posters	 Mass email solicitation	 Telephone
 Letter	 Departmental/Center website	 Television
 Medical record review*	 Departmental/Center research boards	 Newspaper
 Departmental/Center newsletters	 Web-based clinical trial registries	 Clinicaltrials.gov

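### Nine tests across three aims, plus a replication correlation, have no primary outcome, hierarchy or error control, and H2b has a model but no rule for what counts as generalizing

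*Combined protocol and SAP*

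**What the plan says.** The analysis plan stands in two places in the protocol: Section I.4 under *Hypothesis testing*, and Section I.13, Statistical Considerations. The first opens with "Network connectivity strength assessed at each scanning session will be entered into SPSS to test the following Specific Aims" and sets out six sub-hypotheses:

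- **Aim 1.** H1a is measured as the percentage of negative urines from baseline to follow-up scan. H1b is measured by TLFB at one month, with abstinence confirmed by urinalysis.
- **Aim 2.** H2a concerns resting-state network strength. For H2b the text says "This effect will generalize to increased connectivity during fMRI reward and cognitive tasks as in our pilot data". MIDT and Stroop connectivity are assigned to a linear mixed effects model with group and time as factors. Section I.13 agrees: "Opioid abstinence network strength during resting state and task fMRI runs will be compared between time points using linear mixed models".
- **Aim 3.** H3a covers craving and negative affect. H3b correlates change in transfer-run connectivity with change in each.

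Section I.13 adds a replication correlation between baseline network strength and percent opioid-negative urines.

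Neither section names a primary outcome, a significance level for the aims, an order of testing or a multiplicity adjustment. The only trace of a level is in the power statement: "critical t-value=2.10, df=18".

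**The concern.** The tests are presented as hypothesis tests with directional predictions, and the sample is described as adequate for them: "a sample size of N=24 (N=12 per group) is sufficiently powered". With no primary outcome, any one nominally significant result could be reported as the study's positive finding, and a reader could not tell from the plan how many chances it had.

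Two hypotheses also depend on others without the plan saying so. H1b speaks of the reduction persisting, which presupposes the reduction in H1a, yet it can be declared whatever H1a shows. H2b says the resting-state effect carries over to tasks, yet it is not tied to H2a. The stated model has no brain-state factor, and no rule says whether MIDT, Stroop or both must be positive.

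**Working it through.** **1. The plan's own figure.** Section I.13 gives noncentrality 5.36, 18 df, critical t 2.10 and power 0.99 for 10 per group. The noncentral t distribution with these inputs gives 0.999, which agrees with the stated 0.99 to within one percentage point. The 97.5% point of t on 18 df is 2.101 and the 95% point is 1.734, so the power statement used two-sided 5%. I carry that level to the aims as an assumption, because the plan states none for them.

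**2. Count.** H1a 1 + H1b 1 + H2a 1 + H2b 2 (MIDT, Stroop) + H3a 2 (craving, affect) + H3b 2 = 9. The replication correlation makes 10.

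**3. Chance of at least one false positive when every null is true.**

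Independent tests, 1 − 0.95^k:
- k = 9: 1 − 0.95^9 = 0.370
- k = 10: 1 − 0.95^10 = 0.401

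Test statistics with a common correlation (simulated normal statistics, 1,000,000 draws; the correlations are assumed):

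| Tests | ρ = 0.3 | ρ = 0.5 | ρ = 0.7 |
|---|---|---|---|
| 9 | 32.6% | 26.9% | 20.2% |
| 10 | 35.1% | 28.7% | 21.3% |

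For two-sided tests on jointly normal statistics the independent case is an upper limit (Šidák's inequality), so 37% and 40% are ceilings.

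Counting only errors in the predicted direction (2.5% each, independent): 1 − 0.975^9 = 20.4% and 1 − 0.975^10 = 22.4%.

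**4. What a pooled two-task contrast gains for H2b.** If the MIDT and Stroop changes have equal variance and correlate ρ, the SE of their average relative to a single task's is √((1+ρ)/2), and the equivalent sample size is 24 / ((1+ρ)/2):
- ρ = 0.3: √0.65 = 0.81; 24/0.65 = 37
- ρ = 0.5: √0.75 = 0.87; 24/0.75 = 32

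The rest contrast (H2a) gains essentially nothing from the joint fit when data are complete and the state × time term is in the model.

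**5. Cost of Holm in Aim 3.** With four tests the first step is 0.05/4 = 0.0125. For a Pearson correlation with n = 24 (22 df), the critical |r| is t/√(t² + 22):
- at 0.05, t = 2.074: |r| = 0.40
- at 0.0125, t = 2.720: |r| = 0.50

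**The case against.** The strongest reply is that this is a small, first mechanistic study meant to prepare later treatment research, and that correcting across distinct aims is partly a matter of taste. That has some force, and it is why the fix does not ask for one correction over all ten tests. It does not excuse the absence of a primary outcome: the documents nowhere call these tests exploratory, and they describe the sample as sufficiently powered.

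Other objections succeed against stronger readings that a reader might draw:

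- *That H2b has no test.* The documents do not support this. The Aim 2 approach in Section I.4 gives MIDT and Stroop connectivity a mixed model, and Section I.13 repeats it for task runs. What is missing is the deciding contrast and rule.
- *That the trial has a flat 40% chance of a spurious success.* That figure needs ten independent tests at 5%. The aims hold nine; the tenth is labelled replication and tests no neurofeedback effect. The same participants supply every outcome, and Aim 2 measures one network in three states, so some correlation is likely and the figure falls.
- *That one joint model would sharpen all of Aim 2.* Only the pooled task contrast gains, by the amounts in step 4.
- *That a non-significant state × time term would show generalization.* With 24 participants it would not, and a significant one could simply mean a larger effect in the tasks.

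**Conclusion.** The concern holds as a gap in pre-specification. Nine aim tests and one replication test have no primary outcome, order or error control. The chance of at least one false positive is at most about 37% (nine tests) or 40% (ten), and about 20-35% if the tests correlate 0.3 to 0.7. These figures assume two-sided 5% per test, all nulls true and, for the lower range, a common correlation that the documents do not give. Even the lowest is about four times 5%.

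In addition, H1b can be claimed without H1a, and H2b lacks a brain-state factor and a decision rule.

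The test family cannot be settled until a contradiction in the design is resolved. Sections I.1 and I.4 (*Study design*) give active feedback to all 24 participants, while *Hypothesis testing* and Section I.13 compare active with sham, 12 per group. On the all-active reading, H1a as written has no contrast left, because group is its only factor. The count of tests need not change either way.

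**What to change.** 1. Reconcile the all-active design with the active/sham analyses throughout.
2. Name H1a as the single primary test at two-sided 5%, with a contrast that exists in the reconciled design: group if sham is kept, change from baseline if single-arm. Test H1b only if H1a succeeds.
3. Label Aim 2 secondary. Fit one mixed model with brain state (rest, MIDT, Stroop), time and state × time, adding group and its interactions if sham is kept. H2a is the rest contrast. H2b is the average effect over MIDT and Stroop, tested only if H2a succeeds. Report the state × time estimate with its confidence interval as descriptive.
4. Apply Holm to the four Aim 3 tests.
5. Label the replication correlation exploratory.

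This holds each aim to 5%. Across the three aims together the chance of any false positive would still be up to 1 − 0.95^3 = 14%, which is acceptable only because H1a alone is primary and the write-up says so.

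The cost is wording: no new data, visits or participants. The downside is a stricter threshold in Aim 3 (critical |r| up from about 0.40 to 0.50 at the first Holm step), and H1b and H2b claims that depend on H1a and H2a.

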We will utilize connectome-based neurofeedback to assess patterns of functional connectivity within a previously identified “opioid abstinence network”. This network was identified using a whole-brain machine learning approach and predicted subsequent opioid relapse among methadone-maintained individuals. This network was robust, relatively unchanged in follow-up analyses controlling for other clinical variables (e.g., methadone dose, years of opioid use), predicted opioid relapse from different fMRI tasks as well as resting state, and predicted opioid use at multiple time points (two scanning sessions conducted 3 months apart). Design: Individuals on methadone (N=24) will receive active (n=24) connectome-based neurofeedback at 3 weekly scanning sessions (training scans 1-3). Training scans will include both feedback and transfer (i.e. no feedback) runs. Baseline (one week prior to training scan 1) and follow-up (one week following training scan 3) scans will be conducted to test the effects of feedback training on intrinsic connectivity during resting state and fMRI tasks, as in our pilot data. Clinical features of OUD (opioid use, craving, negative affect) will be assessed weekly and at one month follow-up.

Aim 1. To determine if connectome-based neurofeedback is associated with reduced opioid use. Aim 1a. We predict that individuals who receive active feedback will report lower

IRB# 2000025618

levels of opioid use from baseline to follow-up scans. *Aim 1b*. We predict that this reduction will persist over time as assessed at 1-month follow-up.

Aim 2. To determine if connectome-based neurofeedback is associated with changes in intrinsic connectivity. *Aim 2a*. Based on evidence that neurofeedback induces changes in intrinsic connectivity[13], we predict that subjects receiving active feedback will show increased opioid abstinence network connectivity during resting state at follow-up versus baseline scans. *Aim 2b*. We predict that this effect will generalize to increased connectivity during fMRI reward and cognitive tasks at these timepoints.

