
4. **Research Plan:** Summarize the study design and research procedures using non-technical language that can be readily understood by someone outside the discipline. **Be sure to distinguish between standard of care vs. research procedures when applicable, and include any flowcharts of visits specifying their individual times and lengths.** Describe the setting in which the research will take place.

Study design: Participants will receive active ($n=24$) connectome-based feedback at three separate scanning sessions (training scans 1-3). . Training scans will include both neurofeedback and transfer (i.e., no feedback) runs conducted at weekly intervals (**Table 1**).

IRB# 2000025618

Additionally, to test the effects of feedback training on intrinsic

U-Tox	X	X	X	X
TLFB for substance use	X	X	X	X

connectivity, baseline (one week prior to training scan 1) and follow-up (one week following training scan 3) scans will be conducted and will include resting state and reward and cognitive task fMRI runs, to compare networks across brain states as in our prior work[49].

Screening visit: To determine eligibility subjects will first take part in a screening visit involving surveys about their health, smoking, substance use behaviors and attitudes, and the ways in which they view themselves. They will also complete a urine drug test. The screening session will take about 1 and ½ hours. If they are eligible, we will also schedule their MRI appointments during this visit.

Debriefing: At the end of the one month study visit, participants will be fully debriefed by study personnel, who will explain more thoroughly the purpose of the study and answer any questions they may have.

Opioid use: Opioid and other substance use will be monitored weekly at each MRI session from baseline to follow-up using urinalysis and the Timeline Followback (TLFB) [50] method, as in our prior work[10, 48]. Behavioral measures of clinical variables (e.g., pain, other substance use, craving and negative affect) will also be collected.

Imaging Protocol: Scanning will be conducted 2-3 hours following daily methadone on a 3T Siemens Prisma scanner with a 32-channel head coil. A member of the research staff will accompany each subject to the MRRC and stay with them for the duration of the study.

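### Read plainly, H1a's percentage of negative urines includes two samples that predate any possible feedback effect, and the Aim 1 model has no term separating before from after

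*Combined protocol and SAP*

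**What the plan says.** **Outcome.** Section I, 4 (Research Plan), Hypothesis testing, Aim 1 Approach follows opioid use by urinalysis and TLFB "across the five weeks from baseline to follow-up scans and measured as % negative urines (H1a". H1b is separate: it uses TLFB at one month, with urine confirmation.

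**Sampling.** The Opioid use paragraph of the same section states: "Opioid and other substance use will be monitored weekly at each MRI session from baseline to follow-up using urinalysis". Table 1 agrees, marking urine toxicology and TLFB at baseline, training 1-3, follow-up and one month.

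**Timing.** Section I, 1 (Statement of Purpose) states: "Baseline (one week prior to training scan 1) and follow-up (one week following training scan 3) scans will be conducted". Section 4 repeats this. Participants get "connectome-based neurofeedback at 3 weekly scanning sessions (training scans 1-3".

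**Content of the baseline scan.** It has rest, Stroop, monetary incentive delay and one transfer run, and no feedback run. On transfer runs: "Transfer runs will be used to test control of the opioid abstinence network without feedback".

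**Model.** Both section 4 and Section I, 13 (Statistical Considerations) state: "Opioid use will be entered into a linear effects model with the between-subject factor of feedback group (active/sham". Aim 2 adds "the within-subject factor of time (baseline/follow-up scans", and section 13 gives Aim 3 a time factor too. Aim 1 has none, and no baseline covariate.

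**Arms.** Sections 1 and 4 describe 24 participants, all active. Section 13 sizes the study as 12 per group, and the hypotheses in section 4 still compare active with sham.

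**The concern.** A urine or TLFB collected on the day feedback is first given can only report earlier use. The training-1 sample is thus a second pre-feedback measurement, alongside baseline. Averaging both into the outcome adds visits at which active and sham participants cannot differ because of feedback, which pulls the group difference towards zero.

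Without a sham group the consequence is different. Each person contributes one percentage that blends use before and after training. With no group factor to fit and no time term, nothing is left to compare.

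Aim 1 is the clinical aim. Either route could hide a real change in use, or leave the prediction in Aim 1a untested.

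**Working it through.** **1. The plan's own power figure.** Section 13 gives noncentrality 5.36, critical t 2.10, df 18 and power 0.99. With df 18 and two-sided 0.05 the critical t is 2.101. With 10 per group, d = 5.36/√5 = 2.40, and the noncentral t gives power 0.999, consistent with the stated 0.99. That figure concerns differences in networks. The plan gives no power for opioid use, so it neither supports nor contradicts this point.

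**2. Visit calendar.**

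| Visit | Week | Feedback given before this visit? |
|---|---|---|
| Baseline | 0 | no |
| Training 1 | 1 | no |
| Training 2 | 2 | one session |
| Training 3 | 3 | two sessions |
| Follow-up | 4 | three sessions |

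Pre-feedback samples: 2/5 = 40%. Samples that can carry an effect: 3/5 = 60%.

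**3. Raw difference, active minus sham.** Assume feedback raises the share of negative urines by 20 points at each of the last three visits.
- Five samples: (0 + 0 + 20 + 20 + 20)/5 = 12 points.
- Omitting baseline only: (0 + 20 + 20 + 20)/4 = 15 points.
- Last three samples: 20 points.

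**4. If the effect builds.** Assume 1/3, 2/3 and then all of the full effect after one, two and three sessions.
- Five samples: (0 + 0 + 1/3 + 2/3 + 1)/5 = 40% of the full effect.
- Four samples: 2/4 = 50%.
- Three samples: 2/3 = 67%.

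The ratio of the five-sample to the three-sample value is 3/5 in both patterns. The share of the full effect recovered is not constant.

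**5. Allowing for precision.** Five samples are less noisy than three. With equal correlation (ICC) between any two visits, the variance of a k-sample mean is proportional to v_k = ICC + (1 − ICC)/k. The standardised five-sample effect, relative to three samples, is 0.6 × √(v_3/v_5). The documents give no ICC, so the full range is shown. The power columns use 12 per group and two-sided 0.05, with the three-sample d assumed.

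| ICC | Relative effect | N multiplier (1/ratio²) | Five-sample power if three-sample d = 1.2 | Same, d = 0.8 |
|---|---|---|---|---|
| 0 | 0.775 | 1.67 | 0.59 | 0.31 |
| 0.2 | 0.683 | 2.14 | 0.48 | 0.25 |
| 0.5 | 0.632 | 2.50 | 0.43 | 0.22 |
| 1 | 0.600 | 2.78 | 0.39 | 0.20 |

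Power on three samples is 0.80 at d = 1.2 and 0.47 at d = 0.8. The added precision never offsets the dilution. Omitting only the baseline sample gives a ratio of 0.75 to 0.87.

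**6. Using the early samples as a covariate (two-group case).** The residual variance becomes v_3 − ICC²/v_2. At ICC 0.5 this is 0.667 − 0.25/0.75 = 0.333, so the standardised effect rises by √(0.667/0.333) = 1.41. At ICC 0.2 the gain is 1.08, and at ICC 0 there is none.

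**7. Single arm.** With 24 active participants the group factor has one level. The model reduces to a mean percentage of negative urines, which is a level and not a change.

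**The case against.** **The denominator is inferred.** The five-week phrase attaches grammatically to the monitoring, and Aim 1a's prediction about use from baseline to follow-up can be read as change. It stands that the denominator is not spelled out. But with one urine per visit, a percentage has meaning only when pooled over visits, and no text removes a visit or adds a before/after term.

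**The missing comparator is the larger defect.** This stands for the single-arm reading, and a time factor like that of Aims 2 and 3 would remove much of the pooling problem. Any repaired contrast must still say which visits count as before and which as after.

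**The early samples are not wholly untouched.** The baseline transfer run carries the same instruction as the feedback runs, to try strategies that had helped with not using or with craving. This stands in part: the training-1 sample is pre-feedback, but it follows that prompt. The time of day of the training-1 urine is not given, but a same-day sample cannot show later use.

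**The percentage of negative urines is the team's established measure.** In the cited cocaine work it served as an outcome predicted from pre-treatment scans. That use is sound, and section 13's replication correlation can keep it. Testing a change that begins mid-window is a different task.

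**Stronger readings that the documents do not support.** A reader might infer that the plan recovers 60% of the true effect whatever its form; step 4 shows that this needs an immediate, constant effect. A reader might also expect the study to report a within-person fall of 12 points where 20 occurred; the plan never subtracts the pooled percentage from a pre-feedback level. Nor does the protocol label the training-1 sample as on-treatment.

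**Conclusion.** The point holds on the plain reading of the Aim 1 Approach. Two of the five H1a samples reflect use before feedback, and the model has no time or baseline term.

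For the active/sham comparison as written, the difference is 3/5 of what the last three samples would show. The standardised loss is 22% to 40% across all ICCs. This rests on no feedback effect at the first two visits, one urine per visit and equal correlation between visits. The 20-to-12-point illustration also assumes an immediate, constant effect; with gradual build-up, even the three-sample outcome falls short of the full effect.

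For the 24-active design, no dilution factor applies, because there is no contrast to dilute. Aim 1a as written cannot be tested from the pooled percentage. The plan should be changed before analysis.

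**What to change.** In sections 4 and 13:
- Define the H1a outcome as the percentage of opioid-negative urines, and TLFB opioid-use days, from training 2, training 3 and follow-up.
- Define the pre-feedback reference as baseline plus training 1, with TLFB up to the training-1 visit. A sensitivity analysis with baseline alone would cover the prompt given in the baseline transfer run.
- Analyse with a within-person pre/post term, or with the pre-feedback value as a covariate if a sham group exists.
- Reconcile the active/sham text with the single-arm design, so that the Aim 1 model can be fitted.
- State that the replication correlation may keep all samples.

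No new visits or samples are needed, but the analysis itself changes as well as its wording. Two downsides should be stated. The post-feedback value rests on three urines rather than five. And eligibility requires recent opioid use (a positive urine or self-reported past-month use), so a single-arm pre/post change is open to regression to the mean. The second pre-feedback measurement helps show whether use was already falling but does not remove that bias, so the result should be reported as an association.
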